## **B. Description of Population to be Enrolled:**

100 Veterans (50 per group) will be enrolled from Denver VAMC and the University of Colorado Hospital (UCH). Potential participants scheduled for TKA surgery will be identified by a VAMC or UCH surgeon who will refer candidates for study screening. Flyers will also be provided to orthopedic surgeons and health-care providers in the greater Denver metro area. Upon referral and prior to surgery, Veterans will be screened by a research team member, provide informed consent and participate in a pre-operative (PREOP) test session. Consent will be obtained face to face, or with an e-consent. The e-consent will be available to the participant prior to the consent discussion. A qualified study team member will Zoom phone/video call the potential participant. The potential participant will verify their identity. The study team member will explain the consent process and that the participant can navigate forward and backward through the consent form pages and that they may return to the form if later if they want time to think about their participation. The study team member will read the consent form with the participant and will answer all questions that the participant has. The participant and the study team member will both sign and date the consent form and the participant will be able to download or email themselves a copy of the signed form.

Physical activity at PREOP will be quantified as average daily step count (accelerometer-based monitors; see *Accelerometer-based Activity Monitoring* below). To ensure representative physical activity levels between groups, randomization will be stratified using two levels of PREOP step count: <5000 and ≥5000 steps/day. Randomization will also be stratified by decade of age. A research assistant, who is not involved in participant testing/intervention, will manage randomization and maintenance of intervention codes. The study will adhere to the CONSORT statement recommendations for reporting randomized trials (Figure 3).

## CONSORT Flow Diagram

[figure not shown]

Figure 3. Anticipated CONSORT Flow Diagram

Inclusion criteria: 50-85 years of age at enrollment, Veteran, and planned unilateral primary TKA.

Exclusion criteria: severe non-surgical limb pain (pain >5/10 on non-surgical limb with walking); unstable orthopedic, neurologic, or pulmonary conditions that limit physical function; unstable cardiac condition; uncontrolled hypertension; uncontrolled diabetes; acute systemic infection; active cancer treatment; or recent stroke (within 2 years).

Statistical power was estimated using variability estimates from our pilot data collection, where the change in physical activity (steps/day) was assessed in 42 participants (21 receiving intervention, 21 attention control) following TKA. The observed SD of percent change after 3 months of intervention for the pilot sample was 42%, with an effect size of  $d=0.64$ . This effect size equates to a detectable difference of 1,611 steps per day between groups. Based on this expected group difference, a 2-sample, 2-sided t-test at the 5% level with 80 patients (40 per group) would have 80.7% power to detect a group difference. We will enroll 100 participants (50 per group) to allow for a ~20% loss to follow-up. Previous clinical trials in our laboratory, for patients with TKA, have resulted in dropout rates of 4.9% and 6.5% at 3 months post-op and 8.2% and 15.2% at 12 months. Therefore, we are conservatively estimating a dropout rate of 20% at 9 months.

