#### *PAB Pilot Study*

We have recently completed a pilot study to test the feasibility and initial efficacy of the PAB intervention for people undergoing unilateral TKA. In this pilot study, the first version of our PAB intervention (including the behavior-change techniques of education, self-monitoring, tailored feedback, barrier identification, problem solving, action planning, and encouragement) was compared to an attention control group in which patients reported their self-assessed recovery by telephone. Each participant began the pilot study as they were ending conventional outpatient physical therapy. Researchers worked collaboratively with the PAB group participants to create physical activity action plans and promote problem solving for overcoming the individually identified barriers to physical activity. Each PAB participant was given a Fitbit wearable sensor and tablet with a Fitbit application for home use similar to the proposed study (see details Section D.4.5). Intervention duration was 12 weeks with remote sessions conducted once weekly between the participant and researcher. The attention control group had the same frequency and duration of contacts with the researcher over the 12 week period.

Results of the pilot study (n=14 per group) demonstrate the feasibility of the intervention as well as the potential for such an intervention to improve physical activity levels. In terms of feasibility, all participants in the PAB intervention group found the devices and periodic interactions to be acceptable, as measured by a compliance rate of 91% (days of Fitbit use) over the 12 week intervention. No adverse events were reported by any participant in either group.

At the end of the 12-week intervention, the PAB pilot group had an increased step count of 1611 steps/day (PRE:  $5456 \pm 3003$ , POST:  $7067 \pm 3677$  steps/day; mean  $\pm$  SD) compared to 363 steps/day in the control group (PRE:  $5250 \pm 1544$ , POST:  $5613 \pm 2388$  steps/day) (Figure 2). The PAB pilot group had a nearly 2 second improvement in the Timed Up-and-Go test (PRE:  $9.6 \pm 3.1$ , POST:  $7.9 \pm 1.9$  s) compared to 0.6 second improvement in the control group (PRE:  $8.9 \pm 1.0$ , POST:  $8.3 \pm 1.1$  s). The PAB pilot group also increased walking distance by 16.2 m for the 6-Minute Walk Test (PRE:  $136.2 \pm 37.5$ , POST:  $152.4 \pm 26.5$  m)

[figure not shown]

Figure 2. PAB pilot study outcomes.

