Abbreviations: PA, physical activity; TUG, Timed Up-and-Go test; 6MWT, 6-Minute Walk test.

compared to 8.5 m in the control group (PRE:  $143.9 \pm 22.3$ , POST:  $152.4 \pm 25.3$  m). Although under-powered for between-group statistical comparisons, the PAB pilot group improvements represent medium effect sizes (Steps per day,  $d=0.57$ ; TUG,  $d=0.43$ ; 6MWT,  $d=0.70$ ).

The PAB pilot investigation provides initial evidence that daily step count can be improved through a physical activity behavior-change intervention, and these changes are associated with functional improvements. However, a larger scale intervention is necessary to more definitively demonstrate benefits of such an intervention.

Based on the pilot study experiences, the proposed PAB intervention includes two key alterations. First, the PAB intervention will be initiated two weeks after surgery to better integrate the intervention into conventional rehabilitation. Second, the proposed PAB intervention sessions will taper down in frequency from bi-weekly to once monthly across the 12-week intervention period. This approach provides patients opportunity to frequently interact with the therapist during the initial acquisition of the new behavior and promotes participant self-efficacy as they gradually assume more control of managing their behavior with intervention progression.

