## **F. Data Analysis Plan:**

The primary outcome for this study is average number of steps taken per day, as measured by accelerometer-based wearable sensors (activPAL) over a 7-day period at the end of the intervention. This time point is chosen for clinical relevance to establish efficacy of the intervention. Sustainability will be tested as a secondary outcome, by assessing steps taken per day six months after conclusion of the intervention period. Other secondary outcomes include time spent in standing/walking activities and physical function measures. Preliminary descriptive and graphical analyses (including boxplots, scatterplots, profile plots of change over time) will be used for data cleaning, data visualization, and assessing statistical assumptions.

***Primary Analysis (Aim 1):*** The primary analysis will be an intent-to-treat comparison of the differences between the study groups (PAB and CTL) in the change average daily step count from PREOP to POST2 (primary endpoint). Statistical inference will be based on the estimated coefficient for the group variable using an analysis of covariance (ANCOVA) model with change in average daily step count from PREOP to POST2 as the response variable. Additional covariates include the stratification variables (PREOP physical activity and age) to improve the precision of the estimate. The conclusion about group differences will be made based on this single statistical test to control the type I error rate at 0.05. A similar between-group analysis will be performed on the change in daily step count from PREOP to POST3 (6-month effect post-intervention). A sensitivity analysis will be done to evaluate whether conclusions would differ when other covariates are added to the model (e.g., demographics, anthropometrics, comorbidities, psychosocial factors).

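### The 80.7% power comes from percent change in steps, but the primary test is on steps/day, so it is not shown for that test and is probably optimistic

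*Combined protocol and SAP*

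**What the plan says.** The power paragraph (protocol section IV.B, after the CONSORT diagram) takes its inputs from a pilot in which change in steps "was assessed in 42 participants (21 receiving intervention, 21 attention control) following TKA". It reports that "The observed SD of percent change after 3 months of intervention for the pilot sample was 42"%, gives d=0.64, and equates this to 1,611 steps/day between groups. It concludes that "a 2-sample, 2-sided t-test at the 5% level with 80 patients (40 per group) would have 80.7% power to detect a group difference". Enrolment of 100 allows for about 20% loss at 9 months. The same paragraph reports earlier three-month dropout of 4.9% and 6.5%.

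The primary analysis in section IV.F is an ANCOVA "model with change in average daily step count from PREOP to POST2 as the response variable", with PREOP activity and age as covariates. The SAP fits a linear mixed model to average daily step count, with baseline means constrained equal. Neither analyses percent change.

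The PAB Pilot Study part of section III describes 14 participants per group. It says the PAB group's "improvements represent medium effect sizes (Steps per day", d=0.57). It gives a gain of 1,611 steps/day in the PAB arm and 363 in the control arm. On timing, "Each participant began the pilot study as they were ending conventional outpatient physical therapy". In the trial, change is measured from two weeks before surgery to the end of the intervention.

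**The concern.** A standardised effect on the percent scale is a different quantity from one on the steps/day scale. The two agree only under particular assumptions about how change depends on baseline, and the documents state none. The variability input therefore belongs to a variable that the confirmatory test does not use. It also comes from a window that excludes surgery, whereas the trial's window includes it.

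Section IV.F rests the efficacy conclusion on a single test at the 5% level. A null result would be read against a claimed power of about 81%. If that figure does not apply to the test performed, the reader is given too much assurance that an effect of the planned size would have been found.

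**Working it through.** **1. The stated figure.** Two-sample t-test, two-sided 5%, noncentral t with df = 2n - 2 and noncentrality d × √(n/2). With d=0.64 and n=40: df=78, noncentrality 0.64 × √20 = 2.86, power 80.7%. The figure reproduces, so the question is its input.

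**2. What the input implies.**
- On the percent scale, 0.64 × 42% = 26.9 percentage points.
- On the steps scale, 1,611/0.64 gives an SD of 2,517 steps/day.
- The two agree only at a baseline of 1,611/0.269, about 5,993 steps/day. The pilot baselines were 5,456 and 5,250.
- The 1,611 is the PAB arm's own gain. The between-group difference in change is 1,611 - 363 = 1,248. With the implied SD of 2,517, d = 1,248/2,517 = 0.50 and power at 40 per group is 59%.

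The conversion to 1,611 steps therefore does not carry the 80.7% over to steps/day.

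**3. The printed steps/day effect size.** Taking d=0.57 as between-group, in an unadjusted t-test:

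| Completers per group | Power |
|---|---|
| 40 | 71.2% |
| 47 (50 × 0.935 = 46.75) | 78.1% |
| 50 (no loss) | 80.6% |

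**4. Power from the pilot means and SDs.** Inputs: difference 1,248; follow-up SDs 3,677 (PAB) and 2,388 (control). Pooled follow-up SD = √((3,677² + 2,388²)/2) = 3,100. After baseline adjustment, residual SD = 3,100 × √(1 - r²), where r is the pre-post correlation. The documents do not give r, so a range is assumed.

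| Assumed r | Residual SD | Adjusted d | Power, 40 per group | Power, 47 per group |
|---|---|---|---|---|
| 0.5 | 2,685 | 0.46 | 54% | 61% |
| 0.6 | 2,480 | 0.50 | 60% | 68% |
| 0.7 | 2,214 | 0.56 | 70% | 77% |
| 0.8 | 1,860 | 0.67 | 84% | 90% |

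Setting the formula equal to 80.7% and solving for r gives about 0.78 at 40 per group and 0.73 at 47. This approximates the ANCOVA. Power for the SAP's likelihood ratio test was not computed.

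**5. Rebuilding d=0.57.** It cannot be rebuilt from the printed means and SDs without an r. Using the SDs of both visits, 1,248 divided by the pooled SD of change gives d = 0.44, 0.49, 0.56 and 0.66 for r = 0.5, 0.6, 0.7 and 0.8. A between-group reading would thus need r of about 0.7.

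**The case against.** A reader might infer that the trial's true power is 71%. The documents do not support that, for four reasons, all of which stand.

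- **Meaning of d=0.57.** The protocol attaches it to the PAB group's improvements, in a sentence that calls the pilot under-powered for between-group comparisons. It may be a within-group value.
- **Different samples.** It comes from 28 participants, and d=0.64 from 42. Read as between-group effects, their approximate 95% intervals are -0.19 to 1.33 and 0.02 to 1.26. A gap of 0.07 could be noise or an update, so scale is not isolated as its cause.
- **Unadjusted test.** The 71% is for a plain t-test. If d=0.57 applies to change, baseline adjustment at 40 per group gives about 76% to 83% with equal pre and post SDs and r from 0.5 to 0.8, or 71% to 75% with the pilot SDs.
- **Completers.** The 20% loss is for 9 months. At POST2 the earlier three-month dropout suggests nearer 47 per group, where d=0.57 gives 78% even without adjustment.

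A reader might also infer that moving from percent change to steps/day must lower power. That depends on the model. Simulating the plan's percent inputs, with percent change independent of baseline, gives 70% to 75% for baseline-adjusted raw change. A constant additive effect with raw-change d=0.57 and r of 0.6 to 0.8 gives a percent-scale SD of 31% to 52%, which includes 42%, but percent-scale power of only 60% to 62% against 71% for raw change. The documents do not say which model holds.

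None of this supplies a steps/day basis for the 80.7%. If d=0.57 is within-group, the documents print no between-group steps/day effect size at all.

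**Conclusion.** The point holds as a mismatch between the power calculation and the primary analysis. The arithmetic behind 80.7% is correct for its input, but that input is the SD of percent change and the test is on steps/day.

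Probably optimistic is as far as the evidence goes. From the pilot's own difference of 1,248 steps/day, adjusted power runs from 54% to 84% at 40 per group and from 61% to 90% at 47, as the assumed correlation goes from 0.5 to 0.8. The stated power needs a correlation near the top of that range at 40 per group, and somewhat above 0.7 at 47. These figures treat the pilot difference and SDs as the true values and carry them over to a window that spans surgery. The documents support neither assumption directly. No single replacement figure, 71% included, is established.

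**What to change.** - Restate the power in section IV.B on the steps/day scale for the baseline-adjusted analysis. Give the assumed between-group difference and the SD of change in steps/day.
- Show power over a range of PREOP-POST2 correlations and of POST2 completers (40 to 47 per group). Do not print 71% as the adjusted power.
- State whether the 28-person or the 42-person pilot sample supplies the inputs, and whether d=0.57 is between- or within-group.
- State that the pilot's change window began at the end of outpatient therapy, whereas the trial's begins before surgery.

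This changes wording only, and enrolment stays at 100. The SAP is written in the past tense, so the restatement mainly serves interpretation of the result. The cost is a stated power that is less favourable and given as a range.

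### The 1,611 steps/day given as the between-group detectable difference equals the PAB pilot arm's own change and cannot be traced to any reported between-group figure

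*Combined protocol and SAP*

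**What the plan says.** The power paragraph in protocol section IV.B follows the CONSORT flow diagram. It rests on pilot data in which the change in steps/day "was assessed in 42 participants (21 receiving intervention, 21 attention control) following TKA". On variability it says "The observed SD of percent change after 3 months of intervention for the pilot sample was 42" percent, with an effect size of d = 0.64. It then translates that effect size into steps: "This effect size equates to a detectable difference of 1,611 steps per day between groups". The power statement follows directly. "Based on this expected group difference, a 2-sample, 2-sided t-test at the 5% level" and 40 patients per group "would have 80.7% power to detect a group difference". Enrolment is set at 100 to allow for about 20% loss.

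Section III (PAB Pilot Study) describes the pilot with 14 participants per group. There, "the PAB pilot group had an increased step count of 1611 steps/day" (5,456 to 7,067), "compared to 363 steps/day in the control group" (5,250 to 5,613). The effect size given for steps per day at the end of that section is d = 0.57.

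Section F makes the primary comparison the between-group difference in change in daily steps from PREOP to POST2.

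**The concern.** The same four-digit number carries two meanings. In the pilot section it is what one arm gained. In the power paragraph it is what separates the two arms. Because the primary endpoint is a between-group difference in change, the matching pilot quantity is the PAB gain minus the control gain, not the PAB gain alone.

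The detectable difference tells a reader how large an effect the trial was planned to find, and the observed result will be read against it. If 1,611 is really the within-arm gain, the planning effect in steps is overstated by 29% relative to the pilot section (1,611 / 1,248 = 1.29). The power paragraph explicitly presents its power as resting on this expected difference, so the meaning of the number belongs to the sample-size justification.

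**Working it through.** **Inputs.** From section IV.B: d = 0.64, SD of percent change 42%, 40 evaluable per arm, two-sided 5% two-sample t-test, 20% loss. From section III (PAB Pilot Study): means of 5,456 and 7,067 (PAB) and 5,250 and 5,613 (control). From section II, on persistent deficits in physical activity: a mean of 5,886 steps/day attributed to pilot research.

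**1. Reproduce the plan's own figures.** The noncentrality parameter is d × √(n/2) = 0.64 × √20 = 2.86 on 78 degrees of freedom. Two-sided 5% power from the noncentral t is 80.7%, as stated. Enrolment is 80 / 0.80 = 100, as stated. Neither calculation uses 1,611.

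**2. Between-group contrasts in the pilot section.**
- PAB change: 7,067 − 5,456 = 1,611
- Control change: 5,613 − 5,250 = 363
- Difference in change: 1,611 − 363 = 1,248
- Difference in post-intervention means: 7,067 − 5,613 = 1,454

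The power paragraph's figure equals the first line exactly. It equals neither between-group contrast.

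**3. Conversion from the percent scale.** The difference implied by d = 0.64 and a 42% SD is 0.64 × 42% = 26.88 percentage points. In steps this depends on the baseline:

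| Baseline (source) | 26.88% of baseline |
|---|---|
| 5,250 (control, pilot section) | 1,411 |
| 5,456 (PAB, pilot section) | 1,467 |
| 5,886 (section II, pilot research) | 1,582 |

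To reach 1,611 the baseline would have to be 1,611 / 0.2688 ≈ 5,993. No section reports that as a pilot baseline.

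**4. What follows if 1,248 is the design difference.** Power then needs the SD of change in steps/day, which the documents do not give. The SDs below are assumptions, applied to the unadjusted t-test with 40 per arm:

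| Assumed SD of change | d = 1,248 / SD | Power |
|---|---|---|
| 0.42 × 5,456 = 2,292 | 0.545 | 67% |
| 0.42 × 5,250 = 2,205 | 0.566 | 71% |
| 1,248 / 0.64 = 1,950 | 0.640 | 80.7% |

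The first two rows turn an SD of percent change into steps by multiplying by a group mean, which is only approximate. The third row is the SD at which 1,248 steps and d = 0.64 agree.

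**The case against.** The strongest defence is that two data sets are being compared. The power paragraph cites 21 per group and the pilot section 14 per group. No arm means, step difference or baseline are given for the 42-person set, so its between-group difference could be 1,611. This stands, and it is why the point is a probable mislabel rather than a demonstrated miscalculation. Against it, exact agreement to the step with a single-arm change would be a notable coincidence.

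The percent conversion is also open to challenge, because the plan does not say which baseline was used. At 5,886 the result is within 2% of 1,611. The required 5,993 also lies inside the range of means in the table of daily step counts before and after TKA (for example 5,623 overall and 6,071 in the strengthening group preoperatively), though those come from a different study. So an undisclosed conversion cannot be ruled out. What can be said is that no reported pilot baseline yields 1,611.

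Three stronger readings are tempting, and the documents do not support them:
- A reader might infer that the trial is underpowered. The 80.7% follows from d = 0.64 alone, and the illustrative range above includes 80.7%.
- A reader might divide 1,611 by 0.64 to get an SD of 2,517, then find about 59% power for 1,248 steps. That is circular: it accepts 1,611 as a between-group difference to obtain the SD, then rejects it as the difference.
- A reader might treat d = 0.57 and d = 0.64 as contradictory. The first is labelled as steps per day with 14 per group. The second stands beside an SD of percent change with 21 per group. Different scales and samples can give different values. What is missing is any account of how the 28 and the 42 participants relate.

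**Conclusion.** The point holds as one of traceability and probable mislabelling. The detectable difference in section IV.B coincides exactly with a within-arm change in section III, where the between-group difference in change is 1,248 steps/day, and it cannot be rebuilt from the paragraph's own d and SD at any reported pilot baseline. That 1,611 and 1,248 differ in meaning is certain from the pilot section. That the power paragraph took over the wrong one is likely but not proven, since the 42-person results are unreported.

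No power shortfall is established. If 1,248 is the design difference, power runs from about 67% to 80.7% over the assumed SDs of 2,292 down to 1,950, and the true value turns on an SD the sponsor has not stated. These figures are for the unadjusted t-test in the power paragraph. They do not carry over to the covariate-adjusted ANCOVA in protocol section F or the mixed model in the SAP.

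**What to change.** Revise the power paragraph in section IV.B so that the step figure can be traced:
- Name the pilot data set used (28 or 42 participants) and say how it relates to the one in section III.
- State the scale (steps/day or percent change) and the contrast from which d = 0.64 comes.
- Give that set's SD of change in steps/day and the baseline used to convert percent change to steps.
- Then either replace 1,611 with that set's between-group difference in change and give the matching power, or state plainly that 80.7% applies to a 1,611-step between-group difference, which is larger than the 1,248 derived from the pilot section.

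The cost is wording only. The stated detectable difference or its power may look less favourable once the SD is reported. Enrolment and analysis do not change.
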